2.8 Internal pilot study

The **aim** of the internal pilot study will test processes and procedures with planned seamless transition to recruiting to the main trial (64, 65). Participants enrolled in the internal pilot will be included in the analysis of the main trial.

2.8.1 Internal pilot

The nine-month internal pilot phase will be used to test recruitment procedures, confirm and refine recruitment rates, assess protocol compliance, refine procedures for outcome data collection, and test procedures for referral to, delivery of and fidelity with the iRehab intervention. Protocol compliance will be evidenced by the quality and completeness of data returned to the trial office, including baseline and eight-week outcome completion. We will review all data collected to inform

the decision to transition from pilot to main trial. We will evaluate numbers of potential participants approached, reasons for non-eligibility and uptake to the trial to consider accessibility, reach and engagement.

Adherence to standard care and rehabilitation intervention will be assessed during this phase. Uptake and adherence to the active intervention will be evidenced by number of referrals made, number of iRehab intervention sessions attended and reasons for withdrawals amongst those randomised to iRehab intervention. We will monitor time from randomisation to referral to intervention, time from referral to first rehabilitation appointment, number and format of sessions attended and adherence to the programme over six weeks.

2.8.2 Process evaluation: internal pilot

During the internal pilot our process evaluation will explore the intervention in terms of what is working and what is not working, and we will check that our fidelity criteria and procedures enable us to fully assess all aspects of intervention delivery. We will record what standard care has been received at an individual level for all participants across the internal pilot study period. Details of the processes are covered in a Standard Operating Procedure separate to this protocol.

2.8.3 Qualitative interviews

During both the internal pilot phase and main trial, qualitative interviews will allow in-depth exploration of the acceptability of trial interventions. A similar methodology and analytical approach will be used for interviews conducted in the pilot and main trial.

Participants: In the pilot phase, we will invite up to 15 participants taking part in the iRehab intervention for interview, after they have been discharged from the six-week intervention. We will sample participants from a range of recruiting sites, who consented to be contacted for qualitative interview at baseline, striving to interview those of different ages, gender, and ethnicity. We will explore participant views about the perceived helpfulness of the different components of the remote intervention as well as any standard care they have received during this time. Where possible, we will aim to explore reason for discontinuation for any participant who discontinued the intervention before six-weeks. We will interview a sample of participants from the standard care arm to explore their views about their care.

Intervention team: We will interview members of the intervention team, to explore their views about the remote intervention in practice. Staff delivering the intervention will be interviewed during the pilot and main trial. Where possible, at the end of the main trial, we will interview practitioners involved in rehabilitation service delivery in the UK, to explore their views about remote rehabilitation services and the implementation of trial findings.

Trial Staff/ Site research champions: Where possible, we will follow up with trial staff/site champions to explore their views about the trial processes, including recruitment.

Qualitative data collection and analysis: Qualitative data collection and analysis in the internal pilot study will follow the same methodology and plan for analyses as described for the main trial (Section 7.2). Findings from qualitative interviews will be reviewed by the trial team and oversight committees, to inform decision for progression to main trial.

2.8.4 Stop-go criteria

After completion of the internal pilot phase and consideration of recruitment monitoring data and intervention-related data, summary reports will be generated for circulation to oversight committees. The stop-go decision will be made by the funder, following consultation with the TMG, TSC, DMC and NIHR. Data from the internal pilot will inform this decision, from approximately nine months from pilot opening. The recommended traffic light system will be used to guide decisions regarding progression of the trial based on pilot recruitment data, based on an average recruitment rate of 0.8 participants per centre/ per month:

- **Green:** progress from pilot to main trial; review screening logs at sites achieving less than 100%, assess any barriers to recruitment, share strategies from high recruiting sites, review intervention throughput and adherence (see Table 2).
- **Amber:** explore screening logs, assess barriers to recruitment at all sites, share strategies from sites that are recruiting well, open additional sites to recruitment, adaptations to intervention delivery to encourage uptake and adherence.
- **Red:** decision whether to progress to main trial will be made by the DMC, TSC and the NIHR.

Table 2 - Detail of internal pilot phase conducted during first nine months of recruitment, based on opening 16 sites and recruiting n=101 participants

	Red	Amber	Green
Recruitment aim (n=101 participants, up to 16 sites)			
Total number of participants recruited	<50	50-100	101*
Sites recruited	<8	8-15	16
% Threshold	<50%	51-99%	100%
Completeness of outcome measures at 8 weeks (of those recruited to trial*)			
% Threshold of those reaching 8-week timepoint	<75%	75-90%	>90%
Engagement with intervention of those recruited (of those recruited to trial*)			
% Threshold engagement of those allocated to intervention	<50%	51-75%	>75%

* Where engagement with the intervention for the pilot study is interpreted as attendance at first/one session

2.8.5 Process evaluation: Main trial

Embedded process evaluation will continue from the internal pilot throughout the main trial, to explore whether the iRehab and standard care arm interventions were implemented as intended and allow us to understand and explain any factors that may influence trial outcomes (51, 66).

The process evaluation will involve:

- a) Trial process data: ongoing monitoring of trial data will continue from the pilot phase, with evaluation of numbers of people approached, randomised, reasons for non-eligibility, proportion discontinuing from interventions and overall trial attrition. These will be reviewed and discussed at monthly TMG meetings and will allow us to interpret accessibility, reach and engagement.
- b) Intervention fidelity: a sample of recorded intervention sessions from the main trial will be evaluated for quality assessment purposes and intervention fidelity. A checklist will be adapted to monitor intervention fidelity (62,63). Key components will include training and certification of the intervention team to deliver the intervention, monitoring directly throughout the trial and retraining as required (41, 58, 63).
- c) User acceptability survey. Participants in the intervention will be asked about the perceived helpfulness of the different components of the remote rehabilitation intervention using a short questionnaire Theoretical Framework of Acceptability Questionnaire (TFAQ) administered after the intervention. The online platform used for live and recorded exercise sessions will include a single question on satisfaction with session; these data will be collected throughout intervention delivery. Participants in the standard care arm will be asked about their opinion of the care they received at their 8-week follow-up using a short questionnaire (TFAQ) administered via an online link. The questionnaires (TFAQ) could, if preferred, be completed over the phone with a member of the research team or returned via post or email for data entry.
- d) Standard care survey. On completion of trial recruitment and participant follow-up, a single page survey will be sent to all sites to request information on whether any structured rehabilitation was provided over the trial period. This will help us understand usual care in each of the trial sites, and whether this changed over the time during the trial. We will also record what standard care has been received at an individual level for all participants across the trial period.
- e) Qualitative interviews: Qualitative semi-structured interviews will allow in-depth exploration of the acceptability of the intervention and the components.

-Participants. In the main trial, we will conduct an additional 20 semi-structured interviews (n=10 participants from iRehab intervention and n=10 from standard care). Invitation to interview will be after completion of primary outcome data collection, thus from eight weeks onwards. Interviews with participants in the standard care arm will be conducted at a similar time point and will also explore

their views about being in the trial and their care e.g. whether any other strategies for recovery support were sought.

-We will interview the the intervention delivery team to explore their views about the remote intervention in practice and to explore the acceptability of the intervention and the components. Where possible, at the end of the main trial, we will interview NHS staff/academics involved in rehabilitation service delivery in the UK, to explore their views about remote rehabilitation services and the implementation of trial findings.

- Trial staff/ research champions: where possible, we will follow up with site champions to explore their views about trial processes, including recruitment.

Details of the processes are covered in a SOP separate to this protocol.

Qualitative data collection

Optional consent to be approached for qualitative interview will be collected at baseline on entry to the trial. People invited to take part in the qualitative study will receive a separate information sheet about the study and give consent specifically for the interview study. Interviews will be conducted by an experienced qualitative researcher, independent from the intervention delivery team. Interview topic guides will be developed, to ensure similar areas are covered and discussed in each interview. Interviews will be held via video conferencing or by telephone and will be audio recorded, transcribed, and checked for accuracy and anonymity.

For interviews with the intervention team, intervention materials will be referred to, to aid recall and generate discussion. Details of the processes are covered in a SOP separate to this protocol.

Qualitative data analysis

Interview transcripts will be analysed using framework analysis (67).

While each component of the process evaluation will be undertaken and analysed separately, the findings will be triangulated to integrate the qualitative findings and the trial outcomes, and we will explore the mechanistic pathways for any treatment effects (66).

2.8.6 Compliance/contamination

Compliance (adherence) with trial interventions will be monitored throughout the trial. Uptake and adherence to the active iRehab intervention will be evidenced by number of sessions referred to and attended, over the six-week intervention delivery period (41). This is a complex multicomponent individualised intervention, but the expectation is that each participant will engage in at least one intervention session per week over the six-week period. Definitions of full and partial adherence to the iRehab intervention will be refined during the pilot phase informed by data from the process evaluation. We anticipate this to be: full adherence = engaged with five or more sessions (out of six); partial adherence = engaged with one to four sessions; and non-attendance = none.

2.9 Allocation concealment

Participants' treatment allocation is revealed at randomisation via email to the participant themselves and the lead intervention team. Treatment allocation should be concealed from the independent assessor performing the outcome assessments at baseline and follow-up.

At the eight-week and six-month follow-up assessments, participants will be asked to not reveal their allocation to the independent assessor. If allocation is revealed, the assessor will record this on the appropriate CRF.

To minimise performance bias in the intervention arm, the core components will be protocolised to guide overarching delivery, whilst still enabling flexibility for individual participants. The intervention development team will provide training to practitioners, as described in Section 2.5.3 above.

2.10 Concomitant illness and medication

2.10.1 Concomitant illness

We anticipate comorbidity to be high in this post-ICU population. If any illness influences the potential participant's eligibility to participate in the trial (e.g. serious mental health problems that preclude participation in a group intervention) the principal investigator will be informed and a decision reached regarding about whether or not they are eligible to participate. Once recruited and consent has been obtained, if any illness influences the potential participant's eligibility to continue in the trial this will be discussed with the trial team and the participant may need to discontinue treatment and/or withdraw from collection of data.

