Follow-up questionnaires will be completed **remotely online or by telephone** (or postal as exception) at eight weeks and six months, coordinated by WCTU trial office. An email and/or text message will be sent to participants asking them to click on a link which will take them to the online questionnaire portal or they will receive a call to arrange a time to complete the questionnaire verbally via phone. The 30-second sit-to-stand test will be captured by a iRehab researcher using remote consultation and will be conducted as soon as possible aiming to complete it within one week from the completion of the patient reported outcomes. Reminders will be sent to non-responders after two weeks following WCTU processes. The minimum core data set will include the EQ-5D-5L at eight weeks and six months.

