2.6.4 Post-randomisation withdrawals / discontinuation

All participants have the right to withdraw from the iRehab trial at any time if for any reason they change their mind. A participant can discontinue from trial treatment, and they can also choose to withdraw from the trial. There are different levels of withdrawal: a) withdraw consent for future trial involvement b) withdraw consent for future trial involvement and for use of previously entered data. For participants withdrawing completely from the trial, we will retain all data obtained to date of withdrawal, unless the participant explicitly requests for data not to contribute to final analyses.

Wherever possible, we will obtain a reason for discontinuation or withdrawal on trial CRFs although the right of a participant who does not want to give reasons will be respected. For participants wishing

to withdraw from the intervention during the pilot study, we will ask whether they would be willing to explore their experiences of the intervention. There will be a dedicated trial email and helpline which anyone taking part in the trial can access and which will be answered by the WCTU trial team.

Participants may be discontinued from the trial intervention or be withdrawn from the sit-to-stand element of outcome data collection, due to safety reasons, at the discretion of the chief investigator, and lead intervention team (Ulster University/Belfast Health and Social Care NHS Trust).

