6.1 Data collection and management

Trial CRFs and participant questionnaires will be developed to collect all trial data. These CRFs will be developed by the WCTU trial management team in consultation with the CI, statistician, health economist and other relevant members of the trial team.

We will use the standard WCTU web-based application for trial management to record participant data in accordance with the trial protocol. The CRFs will be developed by WCTU team and made available to the participating sites as either paper or electronic CRFs (eCRFs) for ease of data collection; supporting materials will also be available to staff. All documents will be stored safely with restricted access to maintain confidentiality. On all trial-specific documents, other than the consent form, the participant will be referred to by a unique trial-specific number/patient identifier/code in any database, not by name. The trial will be conducted in accordance with the current approved protocol, Good Clinical Practice (GCP), relevant data protection regulations and standard operating procedures (SOPs). A monitoring plan and risk assessment will be devised to protect participant safety

and integrity of trial data. Routine monitoring procedures will be conducted the frequency of which will be determined by each sites rate of recruitment and safety of permitting staff to conduct visits.

Various methods will be used to track missing data including phone, text, and email. Participants will receive a reminder to complete the online questionnaires at each time point alongside a video/telephone call from the independent assessor at WCTU. If a participant has not completed a questionnaire at the follow-up assessment timepoint the independent assessor will encourage them to complete the questionnaire online or provide support for this to be completed via phone (using the reference copy of the questionnaires previously provided). If data remain missing, the independent assessor will make further contact with the participant to attempt to collect the outcome measurements with priority for the core measures.

Data will still be collected for participants who discontinue or deviate from the protocol, unless they withdraw their consent (section 2.1.2). For any participants who do not respond to the follow-up assessment calls or who are known to have died, WCTU will request a death notification form be completed by the recruiting hospital site.

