7.5 Subject population

The primary and secondary analyses will be conducted based on an all-randomised population by intention-to-treat.

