7.6 Procedure(s) to account for missing or spurious data

Whilst every effort will be made to minimise missing data, it is inevitable that some data will be missing. We will monitor the level of and reasons for missingness in the primary outcome. The nature and pattern of missingness will be carefully considered. If deemed necessary, an appropriate imputation method, e.g., multiple imputation, will be applied to impute missing data. The imputed datasets will be analysed as a sensitivity analysis. Further details will be given in the statistical analysis plan.

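### Section 2.10.1 permits illness to end outcome data collection, in conflict with sections 6.1 and 2.6.4, so the primary EQ-5D-5L can go missing because of poor health

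*Protocol*

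**What the plan says.** Four parts of the protocol bear on what happens to outcome data when a participant becomes ill.

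- **Section 2.10.1 (Concomitant illness).** After recruitment and consent, "if any illness influences the potential participant's eligibility to continue in the trial this will be discussed with the trial team". One permitted result of that discussion is put this way: "the participant may need to discontinue treatment and/or withdraw from collection of data". The ground is illness; withdrawn consent is not mentioned. The same section warns: "We anticipate comorbidity to be high in this post-ICU population".
- **Section 6.1 (Data collection and management).** "Data will still be collected for participants who discontinue or deviate from the protocol, unless they withdraw their consent". This is the only exception given.
- **Section 2.6.4 (Post-randomisation withdrawals / discontinuation).** At the discretion of the chief investigator and the lead intervention team, a participant may be taken off the intervention or "be withdrawn from the sit-to-stand element of outcome data collection, due to safety reasons". Questionnaires are not included.
- **Section 7.5 (Subject population).** "The primary and secondary analyses will be conducted based on an all-randomised population by intention-to-treat".

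The EQ-5D-5L is completed remotely, online or by telephone (by post as an exception), and section 2.2.2 gives it priority: "The minimum core data set will include the EQ-5D-5L at eight weeks and six months". On missing data, section 7.6 makes imputation conditional on need and adds: "The imputed datasets will be analysed as a sensitivity analysis".

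**The concern.** Health-related quality of life is the primary outcome, so illness after randomisation is part of what the trial sets out to measure. It is a possible reason to stop exercise or a physical test. It is not in itself a reason to stop asking for a questionnaire that can be completed by telephone. Section 2.10.1 does not make that distinction: it puts treatment and data collection under the same trigger.

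If the sentence is applied as written to a randomised participant, the eight-week EQ-5D-5L is missing for a reason closely tied to its likely value. Data that were never sought cannot be recovered at analysis. Increasing the sample size to allow for loss restores precision, but it does not correct for selective loss.

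**Working it through.** **1. The three rules compared**

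| Section | Trigger | What may stop |
|---|---|---|
| 2.10.1 | Illness bearing on eligibility to continue, after discussion with the trial team | Treatment and/or data collection, without limit |
| 2.6.4 | Safety, at the discretion of the study leads | The intervention, or the sit-to-stand element |
| 6.1 | Withdrawn consent only | Data collection |

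Take a randomised participant who falls ill and does not withdraw consent. Section 6.1 says to keep collecting. Section 2.10.1 permits stopping everything. Section 2.6.4 permits stopping the physical test but is silent on questionnaires. Section 6.1 refers to a section 2.1.2 for withdrawal, but no such section appears in the text; withdrawal is covered in 2.6.4. The cross-reference therefore does not settle the conflict.

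**2. Effect on the analysis population**

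Under section 7.5 such a participant is still in the all-randomised set. The set is unchanged, but the member has no primary outcome. The damage comes through missing data and not through exclusion.

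**3. The plan's own sample size, and whether power is the issue**

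Inputs from section 7.1: difference 0.08, SD 0.2, seven therapists, ICC 0.01, 30% loss, 197 control and 231 intervention. Assumed: two-sided 5% level (from the 95% interval in 7.2.2) and 90% power (stated only for the 15% loss scenario).

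- Evaluable: 197 × 0.70 = 137.9 and 231 × 0.70 = 161.7.
- Design effect in the intervention arm: 1 + (161.7/7 − 1) × 0.01 = 1.221.
- SE = 0.2 × √(1/137.9 + 1.221/161.7) = 0.0243.
- Power = Φ(0.08/0.0243 − 1.96) = 90.8%.

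Working the other way, the smallest design with 90% power needs 134 + 157 evaluable participants, about 415 after inflation by 1/0.70. This is 2.9% below 428, so the stated figure is reproduced closely enough.

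Adding 2, 5 or 10 percentage points of loss in both arms to the 30% gives power of 90.1%, 88.9% or 86.5%. The cost in power is small. What matters is selection.

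**4. Selection, for scale only**

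Let q be the share of an arm withdrawn from data collection for illness, and D their mean utility deficit against those still measured. The arm's observed mean is too high by q × D, and the bias in the treatment difference is q(int) × D(int) − q(ctl) × D(ctl). The protocol gives neither q nor D; every value below is an assumption. Other losses and covariate adjustment are ignored.

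One arm only, D from 0.1 to 0.3:
- q = 2%: 0.002 to 0.006, or 2.5% to 7.5% of 0.08.
- q = 5%: 0.005 to 0.015, or 6% to 19%.
- q = 10%: 0.010 to 0.030, or 12.5% to 37.5%.

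The sign depends on how the two arms compare:
- 5% in the intervention arm only, D = 0.2: +0.010.
- 5% in both arms, D = 0.2 in both: 0.
- 5% in control only, D = 0.2: −0.010.
- 5% in both arms, D = 0.3 intervention and 0.1 control: 0.015 − 0.005 = +0.010.

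**The case against.** The strongest reply is that section 2.10.1 is one loose sentence and should be read in the light of the more specific ones. Section 2.6.4 confines withdrawal for safety to the intervention and the sit-to-stand test. Section 6.1 continues collection after discontinuation and chases missing data, with the core measures first. No sentence says that the EQ-5D-5L stops because of illness. This shows what the authors probably intended, but the wording of 2.10.1 has no such limit and nothing in the protocol ranks one section above another. It could also be read as the participant choosing to withdraw. That fits poorly with language about eligibility to continue, and voluntary withdrawal is already covered in 2.6.4.

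The sentence also starts from consent, not randomisation, and still speaks of a potential participant. Baseline collection lies between the two (sections 2.5.4 and 2.6). Ending data collection in that window raises no intention-to-treat problem. This stands: the concern applies only to use after randomisation.

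Four stronger conclusions are tempting, and the protocol does not support them.

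- A reader might infer that the sickest participants will be removed. The sentence is permissive, and no number is given.
- A reader might infer that it contradicts the all-randomised population. It does not; those withdrawn remain in it without an outcome.
- A reader might infer bias towards the intervention, because that arm reports adverse events weekly (section 5.2.1). Sites report all readmissions (5.5), deaths are reported (5.6), and every participant is asked at assessments (5.2.1). No passage links weekly contact to stopping questionnaires. A difference between arms is plausible but not shown.
- A reader might infer that the planned imputation assumes data missing at random and must fail. Section 7.6 names multiple imputation only as an example, does not state that assumption, and leaves detail to the SAP.

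**Conclusion.** The conflict is real and rests on the protocol's wording alone. Section 2.10.1 permits data collection to end on a ground that section 6.1 does not recognise, and with a reach wider than section 2.6.4 allows. After randomisation this lets the primary outcome go missing because of poor health, which exposes the intention-to-treat comparison to informative missingness.

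The size and direction of any bias cannot be taken from the protocol. Bias towards the intervention would need more such withdrawals in that arm, or a larger utility deficit among those withdrawn there; the reverse pattern would bias towards control. The illustrative shifts depend entirely on assumed shares and deficits. The sample size of 428 is unaffected.

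**What to change.** Reconcile section 2.10.1 with sections 2.6.4 and 6.1:

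- Separate the stopping of treatment, and of the sit-to-stand test as 2.6.4 already allows, from the stopping of outcome collection.
- State that, for randomised participants, the EQ-5D-5L is still sought at eight weeks and six months unless the participant withdraws consent.
- Point the withdrawal cross-reference in 6.1 to 2.6.4.

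Clinical decisions on stopping the intervention or the sit-to-stand test should stay as they are, as should eligibility decisions before randomisation. A sentence confining the consequences of illness to the intervention alone would go too far, because it would contradict the sit-to-stand provision in 2.6.4.

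The cost is about one sentence and a corrected cross-reference in an amendment. Section 6.1 already plans this follow-up, so no extra visits or staff are needed and the sample size does not change.
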